Spontaneous Void Requirements for Patients Undergoing Ambulatory Anorectal Surgery**TABLE OF CONTENTS**

OBJECTIVE	2
BACKGROUND & RESEARCH SIGNIFICANCE	2-3
HYPOTHESIS	3
PRIMARY & SECONDARY OBJECTIVES	3
STUDY PLAN & PROCEDURES	3
INCLUSION/EXCLUSION CRITERIA	3
MEASUREMENT OF STUDY VARIABLES	4-5
STATISTICAL ANALYSIS	5
FUNDING	6
BIBLIOGRAPHY	6

Objective

Urinary retention is a common complication following anorectal surgery and is thought to be multifactorial. Some researchers explain post-operative urinary retention as a consequence of long acting analgesics which dampen the ability for bladder fullness¹. Others point to irritation to pelvic nerves that function with micturition thus blunting pain evoked reflexes^{2,3}. Modifiable factors that have been found to play a role in contributing to post-operative urinary retention include the use of intravenous fluids over one liter during surgery, and administration of local analgesics. Local analgesics provide significant acute pain relief, but contribute to the theory of blunted pain reflexes. Inadequate pain control increases likelihood of urinary retention through inability of perineal relaxation. A balance must be maintained between adequate pain control and interfering with the micturition reflex. Non-modifiable risk factors include age, female sex, the presence of diabetes mellitus, and specific surgical procedure⁴.

Complications of post-operative urinary retention include an increase in urinary tract infections, hospital readmission, damage to detrusor contractility, and for the elderly increased confusion and delirium⁵. The rate of urinary retention post anorectal surgery is between 16-20%. The incidence of urinary retention following high-risk ambulatory surgery is stated to be 5%. The objective of this study is to assess if not requiring patients to spontaneous void prior to discharge from the post-anesthesia care unit (PACU) will result in shorter lengths of stay in the post-anesthesia care unit without increasing hospital readmissions or emergency room visits.

Background & Research Significance

Spontaneous void is a discharge criteria from post anesthesia care units given the potential need for bladder catheterization and prolonged hospitalization for urinary retention. Research evaluating required spontaneous void following ambulatory anorectal surgery is lacking. Research has been conducted on patients requiring spinal and epidural anesthesia which demonstrated that requiring spontaneous voiding post-operation is unnecessary and delays discharge times⁴. Previous research regarding post-operative urinary management of anorectal procedures classified them as 'high-risk' with other procedures⁵. Researchers have sought to address potential risk factors for urinary retention and discuss restriction of pre-operative, perioperative fluid, and adequate pain control to decrease the incidence^{1,2,6,7}. Determining factors that specifically guide discharge for patients undergoing anorectal surgery and the necessity of post-operative void, however, has not been previously evaluated.

Currently the protocol at The Ohio State University Hospital requires voiding spontaneously prior to discharge from the PACU, but operations performed at The Ohio State University Hospital East do not require a spontaneous void prior to discharge. A recent IRB approved study conducted by our group examined if requiring a spontaneous void prior to discharge affects emergency room visits and readmission rates. We conducted a retrospective review of ambulatory anorectal surgeries performed at the two locations. One of these locations required the ability to void spontaneously as a prerequisite for discharge after ambulatory anorectal surgeries (spontaneous void group) whereas the other location did not maintain this requirement

and patients were discharged once they were deemed ready (no void group). Our research concluded that patients can be safely discharged without voiding after anorectal procedures without increasing the risk of ED visits or readmissions. Furthermore, a requirement to spontaneously void before discharge significantly prolongs PACU stays. Thus, we propose to compare PACU discharge times between patients requiring a spontaneous void to those patients not requiring a spontaneous void.

Hypothesis:

Ability to void spontaneously after anorectal procedures does not result in reduced readmissions, emergency room visits and post op complications.

Primary Objectives:

1. To compare readmission and complications rates between patients who are required to void post anorectal surgeries to those who are sent home without voiding spontaneously.
2. To compare the rates of emergency room visit between patients who are required to void post anorectal surgeries to those who are sent home without voiding spontaneously.

Secondary Objectives:

1. To compare PACU times for patients who are required to void post anorectal surgeries to those who are sent home without voiding spontaneously.
2. To compare total hospital costs for patients who are required to void post anorectal surgeries to those who are sent home without voiding spontaneously.

Study Plan and Procedures

This study will be a prospective clinical trial, in which 100 anorectal surgery patients will be randomly assigned to a control (spontaneous void) or experimental (no void) group.

Randomization will be done using the free software provided by www.randomizer.org.

“Spontaneous void” group will include 50 patients who will required to void spontaneously after anorectal surgeries. On the other hand “no void” group will be 50 patients who will be discharged home from the PACU once they meet ambulatory surgery center discharge criteria per hospital guidelines. Patients requiring anorectal surgeries will be consented to take part in the study during the preoperative outpatient office visit. A post op phone call will be made by designated study personnel to participants on post-op day 30 using a study questionnaire to assess re-admission and emergency room visits.

Inclusion Criteria:

1. Age 18-80 years old
2. Patients undergoing hemorrhoidectomy, fistulotomy or anal condyloma excision.

Exclusion Criteria:

1. Age <18 yo or >80 yo
2. Prisoners
3. Pregnant Women

4. Unable or unwilling to follow the study protocol or any reason the research team believes the subject is not an appropriate candidate for this study

Measurements of Study Variables

To achieve the study goals, the following data will be collected:

Pre-operative Data:

1. Demographics: age, sex, height, weight, BMI, race
2. Insurance type
3. Past medical history
4. Diabetes history
5. Hemoglobin A1C
6. Coronary artery disease
7. Chronic obstructive pulmonary disease
8. Inflammatory bowel disease
9. Diagnosis of cancer
10. Renal dysfunction
11. Past surgical history
12. Steroid use
13. Immunosuppression
14. Smoking history
15. Substance abuse
16. Diagnosis
17. ASA class
18. Elixhauser comorbidity index
19. Hospital Cost

Post-Operative:

1. Procedure CPT
2. Where procedure took place
3. Date of procedure
4. Length of procedure
5. Estimated blood loss
6. Reoperation during index admission
7. Diagnosis of Urinary retention
8. Post-operative complications
9. Length of hospital stay in days
10. ICU admission
11. ED visit
12. Readmission
13. Interval to last follow up in days
14. Blood transfusion requirements
15. Total IV fluids received

16. Total pain medicine received
 17. Hospital Cost

Post-Operative Phone Call:

1. Emergency department visit, urgent care visit, or admission outside of The Ohio State University Wexner Medical Center within 30 days post-operative
2. Reason for admission, emergency department visit, or urgent care visit

Schedule of Events

	Pre-Operative Appointment	30 Days Post-Operative
Assess Eligibility Criteria	X	
Informed Consent	X	
Pre-Op Data	X	
Post-Op Phone Call		X
Post-Op Data		X

Statistical Analysis

Data will be expressed using means +/- standard deviations in addition to sample size (n) and percentages. Further statistical analysis will include Students t test for quantitative variables and chi squared test for comparisons of qualitative variables. A p value <0.05 will be used for statistical significance.

Sample Size Calculation:

Power	N1	N2	μ_1	μ_2	$\mu_1 - \mu_2$	σ_1	σ_2	Alpha	Beta
0.80000	50	50	210.0	129.1	80.9	100.0	175.0	0.050	0.20000
0.80000	75	75	210.0	144.3	65.7	100.0	175.0	0.050	0.20000
0.80000	100	100	210.0	153.2	56.8	100.0	175.0	0.050	0.20000

Report Definitions

Power is the probability of rejecting a false null hypothesis.

N1 and N2 are the number of items sampled from each population.

μ_1 and μ_2 are the assumed population means for power and sample size calculations.

$\mu_1 - \mu_2$ is the difference between population means at which power and sample size calculations are made.

σ_1 and σ_2 are the assumed population standard deviations for groups 1 and 2, respectively.

Alpha is the probability of rejecting a true null hypothesis.

Beta is the probability of accepting a false null hypothesis.

Summary Statements

Group sample sizes of 50 and 50 are needed to achieve 80.000% power to reject the null hypothesis of equal means when the population mean difference is $\mu_1 - \mu_2 = 210.0 - 129.1 = 80.9$ with standard deviations of 100.0 for group 1 and 175.0 for group 2, and with a significance level (alpha) of 0.050 using a two-sided two-sample unequal-variance t-test.

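### Comparing total hospital cost by an unadjusted t test carries in operation cost that the void rule cannot change, so the comparison is probably less precise than it could be

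*Combined protocol and SAP*

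**What the plan says.** - Secondary Objectives, item 2, sets the cost comparison: "To compare total hospital costs for patients who are required to void post anorectal surgeries" against those discharged without voiding. The components of the total, the costing source and the time window are not defined.
- Measurements of Study Variables lists cost twice: "19. Hospital Cost" under pre-operative data and "17. Hospital Cost" under post-operative data. Neither is given a role. The Schedule of Events places pre-operative data at the pre-operative appointment.
- Study Plan and Procedures defines the no-void arm as patients "discharged home from the PACU once they meet ambulatory surgery center discharge criteria per hospital guidelines". The arms therefore differ in what is needed to leave the PACU.
- Inclusion criterion 2 admits three kinds of operation: "Patients undergoing hemorrhoidectomy, fistulotomy or anal condyloma excision".
- Statistical Analysis gives one general rule: "Further statistical analysis will include Students t test for quantitative variables and chi squared test for comparisons of qualitative variables". No covariate adjustment is stated there, and no stratification is described under Study Plan and Procedures.
- The only sample size calculation is for a difference in means whose outcome and unit are not labelled. It is not stated to be cost.

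**The concern.** The void rule starts to act when the patient is in the PACU. A total that includes the operation contains a large block of cost already settled by then, and it probably differs between a hemorrhoidectomy, a fistulotomy and a condyloma excision. An unadjusted t test leaves that variation in the standard error. The trial could then show a clear reduction in PACU time together with a non-significant difference in total cost, and the second result could be read as showing that the rule has no cost consequence. A wide interval would not justify that reading. The undefined pre-operative cost item adds a further question about what the total contains.

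**Working it through.** **1. What each part of the total contributes.** Write a patient's total as T = F + L, where F is cost accrued before PACU arrival and L is cost from PACU arrival onward. If theatre care does not depend on allocation, F has the same expectation in both arms, so E(T1) − E(T2) = E(L1) − E(L2). The two comparisons target the same expected difference. Within an arm, Var(T) = σ² + S² + 2rσS, where σ is the SD of L, S the SD of F and r their correlation. This exceeds σ² unless r is below −S/(2σ), so F usually adds variance and removes none except under a sufficiently negative correlation.

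**2. The plan's own figure.** Inputs from Sample Size Calculation: 50 per arm, means 210.0 and 129.1, SDs 100.0 and 175.0, "with a significance level (alpha) of 0.050 using a two-sided two-sample unequal-variance t-test".
- Difference = 210.0 − 129.1 = 80.9.
- SE = √(100²/50 + 175²/50) = √(200 + 612.5) = 28.50.
- Noncentral t with Satterthwaite df 77.9 gives power 80.04%.

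The stated 80% reproduces, as do the rows for 75 and 100 per arm (79.95% and 79.98%). This is not a cost calculation. It is used below only as a scale.

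**3. Illustration of the loss.** Assumptions, none of them in the documents: the sizing figures are PACU minutes; L is proportional to PACU minutes; S is expressed in PACU-minute equivalents. With r = 0 the arm SDs become √(100² + S²) and √(175² + S²). For S = 100, SE = √((20,000 + 40,625)/50) = 34.82, and the variance ratio is 60,625/40,625 = 1.49.

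| S | SE (r = 0) | Variance ratio (r = 0) | Power, r = 0 | Power, r = +0.3 | Power, r = −0.3 |
|---|---|---|---|---|---|
| 0 | 28.50 | 1.00 | 80% | 80% | 80% |
| 50 | 30.21 | 1.12 | 75% | 68% | 83% |
| 100 | 34.82 | 1.49 | 63% | 53% | 77% |
| 200 | 49.12 | 2.97 | 37% | 30% | 48% |
| 300 | 66.43 | 5.43 | 23% | 19% | 28% |

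With SD 100 in both arms and r = 0, power falls from 98% to 95%, 81%, 43% and 24%.

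**4. When later cost is dominated by rare admissions.** Suppose 5% of patients in each arm are admitted, at a cost worth 1,000 PACU minutes each (again an assumption). This adds an SD of √(0.05 × 0.95) × 1,000 = 218 to L. Power for cost from PACU arrival is then 34%, against 30% once F with S = 100 is added. At 2,000 minutes per admission the figures are 14.1% and 13.7%. The gain from leaving F out nearly disappears.

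**The case against.** The strongest reply is that total cost is a legitimate hospital or payer measure, that its expected difference is the same as for later cost, and that nothing in the documents shows how much precision is lost. The first two points stand, so total cost should stay in the report. The third also stands: the illustration depends wholly on an assumed S and r, and step 4 shows that the benefit can be very small.

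It can also be said that theatre care might depend on allocation. The timing of randomisation relative to surgery and any blinding are not stated, and the Objective section names intraoperative fluids and local analgesics as modifiable contributors to retention. If care did differ, a cost clock starting at PACU arrival would miss part of the effect. That is a further reason to report both measures.

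Three stronger readings are tempting, and the documents do not support them:
- *The total includes pre-operative item 19, so cost may be counted twice.* The documents never say that item 19 is part of the total. It could be a baseline value, which might even be used to reduce noise. What is established is only that its role is unstated.
- *A non-significant cost result would mostly reflect the cost of the operation.* Without cost figures this cannot be known. At S = 50 and r = 0 the loss is about five percentage points.
- *The trial is looking for a saving that the total hides.* The objective is neutral, only to compare. Chance imbalance in procedure mix is part of the same variance and is allowed for in the test's error rate.

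**Conclusion.** The concern holds as a loss of precision in a secondary comparison. Total hospital cost, read in its ordinary sense, includes an operation of three possible types that precedes the point where the arms diverge, and the planned test does nothing to remove that variation. The expected difference is unchanged, so there is no bias. This rests on randomisation and on theatre care not depending on allocation.

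The size is unknown. It could be substantial if operation cost varies as much as later cost does, and small if operation cost varies little or if rare admissions dominate later cost. The conclusion does not depend on the illustrative powers, only on the direction in step 1. Separately, the two cost items have no stated role. The primary conclusions on readmission, complications and emergency visits are not affected. It is worth correcting before outcome data are seen, because the change is cheap.

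**What to change.** 1. Pre-specify, under secondary objective 2, a between-arm comparison of hospital cost accrued from PACU arrival to post-operative day 30: PACU stay, any direct admission, and later in-system visits and admissions.
2. Keep total hospital cost and report it alongside, preferably adjusted for procedure type. Procedure CPT is already on the post-operative data list.
3. Define the components and time window of total cost. State the role of item 19 and do not add it to the cost outcome.
4. Report each mean cost difference with a confidence interval, so that a non-significant total is not read as evidence of no cost effect.

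The price is a cost extract split by department or date and one additional secondary cost analysis. No extra patients or procedures are needed.

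### Urinary complications managed at home or in an outside office have no stated planned route into the primary complication rate, and the loss may be greater in the no-void arm

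*Combined protocol and SAP*

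**What the plan says.** The first of the Primary Objectives is "To compare readmission and complications rates between patients who are required to void post anorectal surgeries" and those sent home without voiding. The Hypothesis is that the ability to void "does not result in reduced readmissions, emergency room visits and post op complications", so complications stand apart from readmissions and emergency visits.

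The Objective section names harms that follow from retention: "Complications of post-operative urinary retention include an increase in urinary tract infections, hospital readmission, damage to detrusor contractility", and confusion or delirium in older patients. The Background adds the possible need for catheterisation.

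Study Plan and Procedures describes one contact after discharge, a telephone call "on post-op day 30 using a study questionnaire to assess re-admission and emergency room visits". The Schedule of Events shows no other. Under Measurements of Study Variables, the call has two items. The first is "Emergency department visit, urgent care visit, or admission outside of The Ohio State University Wexner Medical Center within 30 days post-operative". The second asks only why the patient sought that care.

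The post-operative data list, which the Schedule of Events places at 30 days, includes "Diagnosis of Urinary retention" (item 7) and complications (item 8). Neither has a stated source, definition or time window.

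**The concern.** The call asks about visits. It does not ask about inability to pass urine, a catheter, treatment for a urinary infection, or confusion, and it does not ask about care in an office. A patient catheterised or given antibiotics in an outside office, or whose retention resolved at home, can truthfully answer no to the first item, and the second then does not apply.

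By asking about contacts outside the medical center, the plan accepts that its own records will miss outside events. It closes that gap for emergency, urgent-care and inpatient contacts, but not for complications, which are also a primary outcome.

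The arms may not be affected equally. Control patients stay in the PACU until they void, so retention there is seen and can be charted. No-void patients may first meet retention after discharge. If events are missed more often in the no-void arm, its recorded complication rate is too low relative to control, and a finding of no increase could partly reflect what was asked.

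**Working it through.** **The plan's own figure.** The Sample Size Calculation concerns a difference between two means (80.9, SDs 100 and 175, 50 per arm, two-sided alpha 0.05). An unequal-variance t-test with Satterthwaite degrees of freedom gives power 0.8004 against the stated 0.80, so it reproduces. It does not cover the complication rate, and the plan gives no figure on this point to correct.

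**Tracing an event after discharge.**

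| Where the event is managed | Route into the data |
|---|---|
| The hospital's own system | Post-operative items 7 and 8, if taken from the chart (source not stated) |
| Outside ED, urgent care or admission | Call item 1, with the cause from item 2 |
| Outside office | None stated |
| Home, no provider | None stated |

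An event in the last two rows could still be charted if the patient mentions it at an unscheduled contact. Post-operative item 13 records the interval to last follow-up, so some follow-up may occur, but none is scheduled.

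**Events lost per arm.** Inputs:
- n = 50 per arm (Study Plan and Procedures).
- r = retention rate: 16–20% after anorectal surgery, and 5% after high-risk ambulatory surgery (both in Objective). The Background says earlier work classed anorectal procedures as high-risk.
- f = share of cases not recognised before discharge. The documents do not give it; it is set to 1, which makes the results upper figures.
- s = share of those cases left unrecorded. Assumed at 25%, 50% and 75%; it may apply in either arm.

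Expected events = n × r: 50 × 0.16 = 8; 50 × 0.20 = 10; 50 × 0.05 = 2.5.
Lost = n × r × f × s. Recorded rate = r × (1 − f × s).

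| s | Lost of 8–10 (r = 16–20%) | Recorded rate | Lost of 2.5 (r = 5%) | Recorded rate |
|---|---|---|---|---|
| 25% | 2–2.5 | 12–15% | 0.625 | 3.75% |
| 50% | 4–5 | 8–10% | 1.25 | 2.5% |
| 75% | 6–7.5 | 4–5% | 1.875 | 1.25% |

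**Bias between arms.** With the same true rate r in both arms and f = 1, the spurious difference is r × (s in no-void − s in control). It is zero when s is equal. At the extreme where control loses nothing, s of 25%, 50% or 75% in the no-void arm gives a false no-void advantage of:
- 4, 8 or 12 points at r = 16%
- 5, 10 or 15 points at r = 20%
- 1.25, 2.5 or 3.75 points at r = 5%

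**Equal loss.** Borrowing 5% and 16% as true arm rates, purely as an illustration, the true difference is 11 points. Equal s of 25%, 50% or 75% shrinks it to 11 × (1 − s) = 8.25, 5.5 or 2.75 points. Approximate power at 50 per arm falls from 0.43 to 0.33, 0.23 or 0.14. Exact enumeration of the chi-squared test gives 0.45, then 0.32, 0.21 or 0.08.

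**The case against.** **The call is not the only source.** Retention and complications are post-operative items 7 and 8, and the reason item captures an infection, retention or delirium that led to an outside emergency, urgent-care or hospital contact. This stands. A reader might infer that outside events can never reach the complication rate, or that readmission is the only named harm the call can detect. The documents do not support either. The gap is confined to events managed at home or in an outside office that do not reach the hospital's chart.

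**Complications are undefined.** If the term means charted diagnoses, as the wording of item 7 suggests for retention, brief difficulty voiding at home is out of scope and nothing is lost by not asking. This stands in part, so it would be wrong to say the gap exists under every definition. But a catheter placed or an infection treated in an outside office would count under most readings, and neither has a stated route.

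**The questionnaire itself is not in the documents.** Its prompts may be wider than the two listed items. This stands and limits confidence, although the stated purpose of the call agrees with the items.

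**The size is assumed.** The share lost has no basis in the documents, the 16–20% has no stated timing, and control patients can also have later events managed elsewhere. All of this stands: cases recognised before discharge would be charted in either arm, and bias between arms needs the loss to differ.

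**The call matches the overall aim,** which the Objective section frames as readmissions and emergency visits. That is true of the Objective, but primary objective 1 and the Hypothesis both name complications as well.

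**Conclusion.** The point holds, with moderate confidence. Complications are a primary outcome, yet the only scheduled contact after discharge is described as "using a study questionnaire to assess re-admission and emergency room visits" and lists items to match. Retention, catheterisation, urinary infection or confusion managed at home or in an outside office has no stated planned route into the complication rate.

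The documents do not show that the arms are biased relative to each other. A reader might infer that they are, but this requires a larger share unrecorded in the no-void arm. That is plausible, because control patients are observed until they void, but it is not demonstrated. If it occurs, it favours the no-difference hypothesis.

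The loss is at most 2–7.5 of 8–10 events per 50 at 16–20% retention, or about 0.6–1.9 of 2.5 at 5%, for an assumed unrecorded share of 25–75%. These are upper figures because they treat every case as arising unrecognised before discharge.

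**What to change.** Add fixed yes/no items to the existing day-30 call, asked identically in both arms whether or not any visit is reported:

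- unable to pass urine after going home
- urinary catheter placed (where, which day)
- treated for a urinary infection (where, which day)
- new confusion

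Count provider-managed events (catheter placed, infection treated) in the complication rate of primary objective 1, together with charted events, for days 0–30. Report symptom-only answers (inability to void, confusion) separately, by arm and source. State the components, source and time window of complications in the same change.

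The cost is a questionnaire revision and an IRB amendment; no new contact is needed. The main downside is recall at day 30 by patients who know which rule they were under, so reporting may differ by arm. That is why symptom-only answers should stay outside the primary rate. Detrusor damage, also named in the Objective section, would still not be detected.

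### The reason for each return visit and urgent care visits are collected but used in no objective, so an excess of urinary returns after discharge is easy to miss

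*Combined protocol and SAP*

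**What the plan says.** Primary Objectives has two items: "To compare readmission and complications rates between patients who are required to void post anorectal surgeries" and "To compare the rates of emergency room visit between patients who are required to void post anorectal surgeries", each set against patients sent home without voiding. Neither is limited by cause, and neither states a time window. The Hypothesis is that the ability to void "does not result in reduced readmissions, emergency room visits and post op complications". No non-inferiority margin appears anywhere.

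Under Measurements of Study Variables, the post-operative list includes "Diagnosis of Urinary retention" and "Post-operative complications" as separate items. Neither is defined, and the text does not say whether the first counts towards the second. The same list has fields for emergency visits and readmission but none for urgent care.

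The Post-Operative Phone Call items are "Emergency department visit, urgent care visit, or admission outside of The Ohio State University Wexner Medical Center within 30 days post-operative" and "Reason for admission, emergency department visit, or urgent care visit". Study Plan and Procedures describes the purpose of the call as assessing readmission and emergency visits only. Statistical Analysis gives a chi-squared test for qualitative variables in general, and later says that readmission rates and similar categorical variables will be summarised as frequencies. Neither statement mentions the reason for a visit or urgent care.

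**The concern.** Background & Research Significance explains the void criterion by possible catheterisation and prolonged hospitalisation for urinary retention. Dropping it should therefore act mainly on urinary events. Comparing returns for any cause mixes those events with pain, bleeding, wound problems and other returns that the discharge rule is unlikely to change. A patient who goes to urgent care is not counted in the emergency visit or readmission comparison at all.

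Both features make a non-significant result more likely when urinary returns really are higher. Under a no-difference hypothesis without a margin, such a result could be taken as support for leaving out the void. The information that would separate the two kinds of return is already being collected. Deciding which reasons count as urinary after the results are known would not be credible, so the definition has to be fixed beforehand.

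**Working it through.** **1. The plan's own figure.** Sample Size Calculation gives 50 per group, means 210.0 and 129.1, SDs 100 and 175, and two-sided alpha 0.05. The standard error is √(100²/50 + 175²/50) = √(200 + 612.5) = 28.50, and 80.9/28.50 = 2.84. With 77.9 Satterthwaite degrees of freedom, the noncentral t distribution gives 80.04% power, so the stated 80% reproduces. It concerns a difference in means and says nothing about any event rate.

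**2. Inputs for the safety comparison.** From the documents: 50 per arm, chi-squared test, alpha 0.05. Assumed, because the documents give no return rates: urinary returns of 1% (void required) v 8% (no void), and unrelated returns of 5%, 10% or 15% in both arms, in different patients, so that the rates add.

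**3. Precision and power.** The 95% half-width is 1.96 × √{[p₁(1−p₁) + p₂(1−p₂)]/50}, a Wald approximation used here only to compare widths.
- Urinary only: 1.96 × √[(0.0099 + 0.0736)/50] = 8.0 points.
- With 10% unrelated: 1.96 × √[(0.0979 + 0.1476)/50] = 13.7 points.

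Power is by exact enumeration of the two binomial distributions:

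| Outcome | Rates | Uncorrected chi-squared | Fisher's exact |
|---|---|---|---|
| Urinary returns | 1% v 8% | 38% | 14% |
| All returns, 5% unrelated | 6% v 13% | 22% | 11.5% |
| All returns, 10% unrelated | 11% v 18% | 18% | 10% |
| All returns, 15% unrelated | 16% v 23% | 15% | 9% |

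For 1% v 11%, chi-squared power is 60% on urinary returns, against 37%, 29% and 24%. By Fisher's test it is 35%, against 23%, 19% and 17%.

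**4. Effect on the difference itself.** If both kinds of return can occur in one patient, the all-cause rate is 1 − (1−r)(1−b), with r the urinary and b the unrelated rate. At b = 10%, 1% v 8% becomes 10.9% v 17.2%. The difference is 6.3 points, which is 7 × (1 − 0.10). The absolute difference shrinks little; the loss is mostly in precision.

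**5. Less extreme rates.** Objective quotes retention rates of 5% and 16–20%. These are not return rates, but used purely as an illustration (5% v 16%), normal-approximation power falls from 43% to 31% with 5% unrelated returns and to 24% with 10%.

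**6. Uncounted urgent care.** Assume 1% v 10% urinary returns and 5% unrelated, so 6.0% v 14.5% in all and 29% power (normal approximation). If a quarter of urinary returns go to urgent care and are not counted, the rates become 1 − (1 − 0.0075)(0.95) = 5.7% and 1 − (1 − 0.075)(0.95) = 12.1%. The difference falls from 8.55 to 6.4 points and power to 20%. If half go there, power is 12%. The urgent care share is also an assumption.

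**The case against.** The strongest reply is that retention already has a way into the primary comparison. Complications are part of the first primary objective and of the hypothesis, the Objective section describes urinary retention as a common complication, and a retention diagnosis is collected. A reader might infer that safety rests only on emergency visits and readmissions; the documents do not support that. Nor do they state an all-cause or a 30-day endpoint. Both are inferred from the absence of a restriction and from the timing of the call.

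This reply stands in part, but the complications route is no substitute. Retention has no definition or window, and one arm must void in the PACU while the other need not. Retention found there depends on that check. It could raise the void-required arm's rate and make omission look safer. It is not a fair between-arm measure of harm after discharge.

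Three further replies are sound. The chi-squared advantage depends on the test: at 1% v 8%, about 4.5 events are expected in total, and by Fisher's test the gap nearly closes. The chosen rates, with a control rate near zero, favour the cause-specific outcome. And sample size is the larger problem, since every cause-specific power shown is below 80%. The general chi-squared statement could also cover visits grouped by reason, but it names no such endpoint and does not say which reasons count.

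The documents also give no share of patients using urgent care. The words limiting the phone item to outside facilities may be meant for admissions only. If they apply to all three items, urgent care within the medical center has no listed field.

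**Conclusion.** The point holds as a gap in prespecification. The plan collects what it needs to isolate urinary returns after discharge, and uses it nowhere. Under the assumed 1% v 8%, with 10% unrelated returns, isolating them narrows the interval half-width from 13.7 to 8.0 points. The power gain is 18% to 38% or 10% to 14%, depending on the test. All of these rest on assumed rates.

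A reader might infer that unrelated returns pull the estimated difference itself close to zero, or that a cause-specific outcome would make the trial adequate for safety. Neither follows. Unrelated returns reduce the absolute difference only by the factor (1−b), although uncounted urgent care visits do remove events from it. With 50 per arm, a urinary excess of this size would still usually be missed. The change is worth making because it is cheap and improves precision on the harm that the void rule targets.

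**What to change.** Keep the existing outcomes and add one prespecified secondary objective: any unplanned emergency, urgent care or hospital return, at any facility, after discharge and within 30 days of surgery, for a urinary reason (retention, catheterisation or urinary infection). List the qualifying reasons in advance and have them classified without sight of the arm. Report the risk difference with a 95% confidence interval suited to small counts, such as Newcombe or Miettinen–Nurminen rather than Wald, and state that a non-significant result will not be read as evidence of safety.

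Reword the phone item so that urgent care at any facility is captured. Define complications, say whether a retention diagnosis counts and over what window, and separate retention found before discharge from retention found after it. Reconcile the chi-squared statement with the one that only summarises readmission as frequencies.

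The cost is one more reported outcome, a small change to the questionnaire wording and classification of a handful of visits. The reason for each visit is already on the form.
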